## 2.10 CCI [REDACTED]

CCI [REDACTED]

Table 2-2 CCI [REDACTED]

CCI [REDACTED]

CCI

CCI

Table 2-3

CCI

CCI

CCI

2.11

CCI

CCI

CCI

## **2.12 Interim analysis**

CCI

## **3 Sample size calculation**

CCI

## **4 Change to protocol specified analyses**

CCI

## 5 Appendix

### 5.1 Imputation rules

The below imputation rules will be used for the analyses.

#### 5.1.1 Study drug

No imputation will be made to the start date and end date of study treatment.

#### 5.1.2 AE date imputation

The below tables ([Table 5-1](#) and [Table 5-2](#)) are for the imputation techniques for the dates of adverse events, concomitant medications and other safety assessment dates.

**Table 5-1 Imputation of start dates and time for AE, CM**

Missing Element	Rule
Day, month, and year	No imputation will be done for completely missing dates
Day, month	If available year = year of study treatment start date, then start date = 01JanYYYY if stop date contains a full date, and stop date is earlier than study treatment start date, else set start date = study treatment start date. If available year > year of study treatment start date, then 01JanYYYY. If available year < year of study treatment start date, then 01JulYYYY.
Month	If start date year is equal to treatment start year and the stop date is earlier than treatment start, then MONTH =01, else MONTH = TREATMENT MONTH.
Day	If available month and year = month and year of study treatment start date, then set start date= 01MONYYYYYif stop date contains a full date and stop date is earlier than study treatment start date, . else set start date = study treatment start date. If available month and year > month and year of study treatment start date, then 01MONYYYYY. If available month and year < month year of study treatment start date, then 15MONYYYYY.
Time	If time is missing, then start time will be imputed by 23:59

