8.2 Participant demographics/other baseline characteristics

Country-specific regulations should be considered for the collection of demographic and baseline characteristics in alignment with CRF.

Participant demographics: age (in years), sex, race/predominant ethnicity (if permitted) and relevant medical history/current medical conditions (until date of signature of informed consent) will be recorded in the eCRF. Participant race/ethnicity data are collected and analyzed to identify any differences in the safety and/or efficacy profile of the treatment due to these characteristics. In addition, these data are necessary to assess the diversity of the study population as required by health authorities.

All prescription medications, over-the-counter drugs and significant non-drug therapies prior to the start of the study must be documented up to 6 months before the study. See also the protocol [Section 6.8.1](#) Concomitant Therapy for further details on what information must be recorded on the appropriate page of the eCRF.

To determine the eligibility for inclusion in the study, serum creatinine, eGFR and surgery information will be collected and recorded in the eCRF.

8.2.1

CCI

CCI

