### **2.4.2 Prior, concomitant and post therapies**

The safety analysis set will be used for the analyses below.

Data for concomitant medications and non-drug therapies will be listed by treatment group and participant.

Concomitant medications and non-drug therapies will be summarized according to the Anatomical Therapeutic Chemical (ATC) classification system, by treatment group and following period.

- Pre-operative period: The screening period i.e., from the date of ICF to immediately before surgery.
- Post-operative period: The period starts from study drug infusion to end of study.

The concomitant medications or therapies administered will also be summarized for the overall period by ATC class and treatment group.

A separate summary will be created for vasoactive agents which is getting administered during peri-operative period i.e., period during the surgical procedure itself, and immediately post-surgery until start of study drug infusion. A separate listing will be created for vasoactive agents.

CCI

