**Table 5-2 Imputation of end dates and time for Adverse Events and Concomitant Medications**

Missing Element	Rule
Day, month, and year	Completely missing end dates (incl. ongoing events) will be imputed by the end date of the on-treatment period* or EOS date, whichever is earlier
day, month	If partial end date contains year only, set end date = 31DecYYYY or end date of the on-treatment period *, whichever is earlier
Day	If partial end date contains month and year, set end date = last day of the month or end date of the on-treatment period*, whichever is earlier
Time	If time is missing, then end time will be imputed by 00:00 (24hr clock)

\* last treatment group date plus 30 days not > (death date, cut-off date, withdrawal of consent date)

Any AEs and ConMeds with partial/missing dates will be displayed as such in the data listings.

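### Two start-date rules in SAP Table 5-1 give wrong or impossible dates as written, and using the same table for medications can leave some ongoing medicines out of the pre-operative summary

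*SAP*

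**What the plan says.** SAP Table 5-1 imputes start dates for adverse events and for concomitant medications; section 5.1.3 refers back to it for the latter. Its rows differ in how they protect the dose date.

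- *Day, month* row (only the year known). A start in the dose year goes to the dose date, except that it goes to 1 January "if stop date contains a full date, and stop date is earlier than study treatment start date". A later year gives 1 January of that year. For an earlier year: "If available year < year of study treatment start date, then 01JulYYYY".
- *Day* row (month and year known). It works the same way within the dose month and has the same full-stop-date condition. For a later month: "If available month and year > month and year of study treatment start date, then 01MONYYYYY".
- *Month* row (day and year known). If the year is the treatment year and "the stop date is earlier than treatment start, then MONTH =01, else MONTH = TREATMENT MONTH". Nothing further is said.

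Table 5-2 imputes partial stop dates: "If partial end date contains month and year, set end date = last day of the month", or the end of the on-treatment period if that is earlier. SAP 2.7 and 2.7.1 count an event as treatment-emergent if it starts from Day 1 (or worsens), within an on-treatment period that ends at end of study. SAP 2.4.2 summarises medications by period. The first is defined as "Pre-operative period: The screening period i.e., from the date of ICF to immediately before surgery"; the post-operative period runs from infusion to end of study. There is also an overall summary.

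**The concern.** Imputed start dates decide whether an incompletely dated event enters the treatment-emergent tables and which period table a medicine enters. The *Month* row omits two protections that the adjacent row has, so knowing the day as well as the year can give a worse date than knowing the year alone. Its error can remove real on-study events, which is the unsafe direction in a trial with safety as a secondary objective. The full-stop-date condition does the reverse: it discards a recorded stop month that proves the event was over before dosing. For medications, sending an unknown start to the dose date is not a cautious default, because it takes background treatment out of the pre-operative picture.

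**Working it through.** The plan gives no figure for this, so I applied the rules literally to examples and then enumerated them.

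**Inputs.** Study day = date − dose date + 1 (SAP 2.1.1). Follow-up is to Day 90. Screening is within 30 days before surgery (Protocol 4.1), and adverse events are collected from consent (Protocol 8.6.1). Assumptions: dose dates uniform over a calendar year, and onset uniform over the stated window. The documents do not say how often each missing pattern occurs.

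**(a) Month row, later year.** Dose 15Nov2023, so Day 90 is 12Feb2024. Onset 10-UNK-2024 can be on study only as 10Jan2024 (Day 57) or 10Feb2024 (Day 88). The rule gives 10Nov2024: 361 + 1 = Study Day 362. With the day also missing, the *Day, month* row would give 01Jan2024, which is on study.

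**(a) Month row, same year.** Dose 20Jun2024, so Day 90 is 17Sep2024. Onset 05-UNK-2024, ongoing, becomes 05Jun2024, before the dose. The dates 05Jul (Day 16), 05Aug (Day 47) and 05Sep (Day 78) are equally open.

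**(a) Enumeration, true onset on study, only the month missing (365 dose dates in 2023).**

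| True onset | Records | Put before dose | Put after Day 90 | Not a valid date | Inside window |
|---|---|---|---|---|---|
| Days 1-90 | 365 × 90 = 32,850 | 13,035 (39.7%) | 3,977 (12.1%) | 316 (1.0%) | 15,522 (47.3%) |
| Days 1-8 | 365 × 8 = 2,920 | 308 (10.5%) | 28 (1.0%) | 0 | 2,584 (88.5%) |

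The share outside the window is 39.7% + 12.1% ≈ 52% for Days 1-90 and (308 + 28)/2,920 = 11.5% for Days 1-8. A non-valid date arises when the known day does not exist in the dose month. The *Day* and *Day, month* rows put none of the true on-study onsets on the wrong side of the dose.

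**(b) Partial stop date.** Dose 15Nov2023, start 2023, stop Oct 2023. The stop is not a full date, so the start becomes 15Nov2023. Table 5-2 sets the end to 31Oct2023. The event counts as treatment-emergent and ends before it starts. The case is feasible, since consent could be as early as 16Oct2023. I enumerated 2024 dose dates with one-day events starting 30 to 2 days before dosing. With a full stop date, 0% are put on or after the dose in any row. With a start year only and a stop month before the dose month, 91.7% are put on the dose date.

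**(c) Ongoing medicine begun before surgery.** If the start is incomplete at the level of the dose year or dose month, it is set to the dose date. A missing time becomes 23:59, so the medicine misses the pre-operative period.

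- Year only, begun 1-180 days before dosing: 49,410/65,700 = 75.2% set to the dose date.
- Day missing, begun 1-30 days before: 5,373/10,950 = 49.1%.
- Either pattern, begun 366-1,095 days before: 0%.

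All percentages are shares of records with that pattern, not of all records.

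**The case against.** - **Rare patterns.** A date with a known day and year but no month is unusual, start and end dates must be reported (Protocol 8.6.1), and missing values are queried (Protocol 10.1.5.2). This stands and limits the size. A reader might infer from the 52% that about half of all treatment-emergent events would be lost. The documents do not support that: the figure holds only within one missing pattern, and under uniform onset to Day 90. Participants are followed daily on Days 2-8, and early onset brings it down to 11.5%.
- **Narrow window for (b).** The event must begin and end between consent and dose, at most 30 days, with both dates partial. This stands. Sending an uncertain start to the dose date is also a fair cautious convention for adverse events, but it does not justify an event that ends before it starts.
- **Medications.** A reader might infer that chronic medicines in general appear as new treatment after dosing. The documents do not support that. Medicines begun in an earlier calendar year are placed before the dose. An ongoing medicine belongs in the post-operative summary anyway, and no table of new starts is visible. The overall summary still counts it, and listings show partial dates as recorded. The requirement in Protocol 8.2 that prior medications "must be documented up to 6 months before the study" is a documentation span, not a limit on when a medicine began. SAP 5.1.3.1 calls prior-therapy imputation not applicable, and SAP 5.1.3.3, on other imputations, is redacted and may change how the table applies. What remains is omission from one table, on the visible text.
- **Equal application.** The rules are the same in every arm and do not touch the creatinine endpoint. This stands.

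**Conclusion.** Points (a) and (b) hold on the unredacted text: followed literally, the rules give a Study Day beyond the end of the trial, non-existent calendar dates, and events that end before they start. Point (c) holds only for ongoing medicines begun before surgery in the dose year or dose month with a start date incomplete to that level, and only for the pre-operative summary. It also depends on the redacted subsection not already dealing with it.

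For (a), 11.5% to 52% of true on-study onsets with only the month missing fall outside the window, depending on the onset distribution assumed. The number of such records is unknown and probably small. The effect is confined to descriptive adverse event and medication summaries. Severity: minor.

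**What to change.** In Table 5-1:

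1. *Month* row: for a later year, use January and keep the known day. In the dose year, if the imputed start falls before the dose and the stop is not known to precede it, use the dose date. Never let the start exceed the stop date or end of study, and say what to do when the day does not exist in the month.
2. All rows: compare the latest date consistent with a partial stop date with the dose date, instead of requiring a full stop date.
3. Medications: assign the pre-operative period from the known date parts and any CRF information that the medicine was taken before surgery, not from the adverse event default. Do not simply use the earliest consistent date. For year-only starts truly on Days 1-90 that would place about 88% before the dose, and about 99% for Days 1-8, so post-operative medicines would enter the pre-operative table.

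The cost is a few lines of SAP text and programming. Item 1 will count a few pre-dose events as treatment-emergent, as the other rows already do. Item 3 needs a rule for medicines whose use before surgery cannot be established.

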**Table 5-2 Imputation of end dates and time for Adverse Events and Concomitant Medications**

Missing Element	Rule
Day, month, and year	Completely missing end dates (incl. ongoing events) will be imputed by the end date of the on-treatment period* or EOS date, whichever is earlier
day, month	If partial end date contains year only, set end date = 31DecYYYY or end date of the on-treatment period *, whichever is earlier
Day	If partial end date contains month and year, set end date = last day of the month or end date of the on-treatment period*, whichever is earlier
Time	If time is missing, then end time will be imputed by 00:00 (24hr clock)

\* last treatment group date plus 30 days not > (death date, cut-off date, withdrawal of consent date)

Any AEs and ConMeds with partial/missing dates will be displayed as such in the data listings.

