9.4.1 Safety endpoints

For all safety analyses, the safety set will be used. All listings and tables will be presented by treatment group.

Safety summaries (tables, figures) include only data from the on-treatment period with the exception of baseline data which will also be summarized where appropriate (e.g. change from baseline summaries). In addition, a separate summary for death including on treatment and post treatment deaths will be provided. In particular, summary tables for adverse events (AEs) will summarize only on-treatment events, with a start date during the on-treatment period (treatment-emergent AEs).

The on-treatment period lasts from the date of first administration of study treatment to 90 days (EOS) after the date of actual administration of any study treatment.

Adverse events

All information obtained on adverse events will be displayed by treatment group and participant.

The number (and percentage) of participants with treatment emergent adverse events (events started after the first dose of study medication or events present prior to start of blinded treatment but increased in severity based on preferred term) will be summarized in the following ways:

- by treatment, primary system organ class and preferred term.
- by treatment, primary system organ class, preferred term and maximum severity.

Separate summaries will be provided for study medication related adverse events, death, serious adverse events, and other significant adverse events leading to discontinuation.

The number (and proportion) of participants with adverse events of special interest will be summarized by treatment group.

A participant with multiple adverse events within a primary system organ class is only counted once towards the total of the primary system organ class.

Vital signs

All vital signs data will be summarized by treatment group and visit/time and if ranges are available, abnormalities (and relevant orthostatic changes) will be flagged. Summary statistics will be provided by treatment group and visit/time for raw and change from baseline.

12-lead ECG

PR, QRS, QT, QTcF, and RR intervals will be obtained from 12-lead ECGs for each participant during the study. **CCI**

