## **2.7 Safety analyses**

For all safety analyses, the safety analysis set will be used. All listings and tables will be presented by the treatment group.

Safety summaries (tables, figures) will show events that started on Study Day 1 (including data collected for events prior to start of treatment, i.e. intra-surgery, as well as post start of treatment, i.e., post-surgery), and events that started on Study Day 2 and later. Baseline data, which may have been reported on Study Day 1 prior to surgery or on Day of Screening, will also be summarized where appropriate (e.g., change from baseline summaries), utilizing Day 1 data whenever available for both days. In addition, a separate summary for deaths including on treatment and post treatment deaths will be provided. In particular, summary tables for adverse events (AEs) will summarize only on-treatment events, with a start date during the on-treatment period i.e., from Day 1 (treatment-emergent AEs).

The on-treatment period lasts from the date of first administration of study treatment until EOS (i.e., D90 or date of last study visit in the event of early study discontinuation).

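### SAP Table 5-2 ends the on-treatment period at Day 31 instead of Day 90, and the missing-time defaults run backwards, so some incomplete records get an end before their start

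*SAP*

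**What the plan says.** **End of the on-treatment period.** SAP 2.7 states: "The on-treatment period lasts from the date of first administration of study treatment until EOS (i.e., D90 or date of last study visit" (the sentence goes on to cover early discontinuation). Protocol 9.4.1 agrees in substance: "The on-treatment period lasts from the date of first administration of study treatment to 90 days (EOS". The footnote to SAP Table 5-2 gives the same term a different end: "last treatment group date plus 30 days not > (death date, cut-off date, withdrawal of consent date".

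**Where the footnote acts.** Table 5-2 says: "Completely missing end dates (incl. ongoing events) will be imputed by the end date of the on-treatment period", or by the EOS date if that is earlier. Partial end dates are also capped at the footnote date. SAP 5.1.2 applies the tables to adverse events, concomitant medications and other safety assessment dates.

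**Missing times.** Table 5-1: "If time is missing, then start time will be imputed by 23:59". Table 5-2: "If time is missing, then end time will be imputed by 00:00 (24hr clock". No readable rule stops an imputed end from falling before the start.

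**Where clock time could matter.** SAP 2.4.2 sets a pre-operative period that stops just before surgery and a post-operative period that begins at infusion. It also plans a separate vasoactive-agent summary for the "period during the surgical procedure itself, and immediately post-surgery until start of study drug infusion". These boundaries all fall on Day 1.

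**The concern.** A single term has two incompatible definitions, and the one in the imputation table always gives the earlier date for a participant who completes follow-up. A programmer who follows the text gets impossible intervals. One who notices has to make a correction that the SAP does not document.

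The time defaults are a separate fault. They place an unknown start at the last minute of the day and an unknown end at the first, which is the wrong way round for any record that starts and ends on one date.

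At stake are derived end dates and durations, and possibly the placement of untimed Day 1 medications (vasoactive agents in particular) before or after surgery and infusion start.

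**Working it through.** **Inputs**
- One infusion, on Day 1 (protocol 6.4; SAP 2.1.1). The footnote's wording about the last treatment group date is unclear; with one infusion, the only reasonable reading is the dose date.
- Study day = date − first dose date + 1 (SAP 2.1.1).
- EOS visit at Day 90 ±7, so Day 83 to Day 97 (protocol 1.3).
- End-date and time rules from SAP Tables 5-1 and 5-2.

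**1. The two period ends.** Footnote: 30 + 1 = Study Day 31. Against Day 90 in SAP 2.7 the gap is 90 − 31 = 59 days. Over the visit window it is 83 − 31 = 52 to 97 − 31 = 66 days. Read literally, the protocol's 90 days after administration is Day 91, a gap of 60.

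**2. Ongoing or completely missing end date.** Imputed end = min(31, EOS day) = 31 for anyone who reaches Day 90, so the EOS branch never applies to them.

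| Start (study day) | Imputed end | End − start (days) | End − start if the period ends at Day 90 |
|---|---|---|---|
| 5 | 31 | +26 | +85 |
| 31 | 31 | 0 | +59 |
| 32 | 31 | −1 | +58 |
| 45 | 31 | −14 | +45 |
| 60 | 31 | −29 | +30 |
| 90 | 31 | −59 | 0 |

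**3. Partial end date.** Take an illustrative dose on 1 March. An event starts on 20 April (Day 51) and its end is recorded only as May. The rule gives min(31 May, 31 March) = 31 March (Day 31), which is 20 days before the start.

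**4. Missing times, same-day record**
- Both missing: 00:00 − 23:59 = −23 h 59 min.
- Start missing, end 14:00: 14:00 − 23:59 = −9 h 59 min.
- End missing, start 10:00: 00:00 − 10:00 = −10 h.
- With one time missing, 1439 of the 1440 possible known minutes put the end before the start.
- Both missing but ending the next day: 24 h − 23 h 59 min = 1 minute. The record is shortened, not reversed.
- With the defaults swapped, the first case becomes +23 h 59 min.

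**5. Day 1 medications.** Consider a vasoactive drug given during surgery, started and stopped on Day 1 with no times. It is imputed to start at 23:59, after an infusion begun earlier that day, and to end at 00:00, before surgery. The readable part of SAP 2.4.2 does not say how records are assigned to periods. If start time decides, the drug becomes post-operative. If overlap decides, it falls in none of the three periods. Both outcomes are conditional on imputed times being used for the assignment.

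**The case against.** The strongest reply is that no readable output is shown to use the wrong values. Most of it stands.

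- **Adverse event counts.** Treatment-emergent status rests on the start, and SAP 2.7 splits the periods by start on Day 1 versus Day 2 onward. SAP 2.7.1 adds that second-period events end by Day 90, but an imputed Day 31 and an imputed Day 90 both satisfy that. No table of event durations is visible.
- **Listings.** Partial or missing dates are shown as recorded.
- **Creatinine.** A reader might infer that misplaced vasopressor times threaten the primary result. The documents do not support this: the primary question is posed regardless of concomitant medication, and the visible model terms in SAP 2.5.2 are baseline creatinine, treatment, age and eGFR.
- **Vasoactive summary.** The protocol collects vasopressor use with the surgery information (protocol 1.3), and SAP 1.1 intends Day 1 data to be separated by surgical phase where possible. Misplacement is therefore a possibility, not an established result.
- **Scale.** A reader might take 59 of 90 days (66%) as the share of events affected. It is a share of calendar days. Records with complete dates and times are untouched, and no rate of incomplete records is given.
- **Redaction.** SAP 4 and 5.1.3.3 are blacked out and could hold an overriding rule.

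What the reply does not remove is the contradiction between the footnote and 2.7, or the reversed time defaults. An override elsewhere would still leave the visible footnote needing correction.

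**Conclusion.** The point holds as a fault in the written derivation rules. The footnote contradicts SAP 2.7 and protocol 9.4.1 by 59 days (52 to 66 over the visit window). Taken literally, it gives a negative interval to every ongoing or incompletely dated record that starts after Day 31, and it cuts earlier ongoing records at Day 31. The time defaults independently reverse nearly every same-day record with a missing time, and can misplace untimed Day 1 medications in the SAP 2.4.2 summaries.

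This rests on reading the footnote's date as the dose date and on there being no override in the redacted sections. It is worth correcting because the rules are wrong as written and the repair is cheap. It does not call the adverse event incidence tables, the listings or the visible primary analysis into question.

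**What to change.** 1. Change the Table 5-2 footnote so that the on-treatment period ends at EOS (Day 90) or the last study visit, and not later than death, cut-off or withdrawal of consent, to match SAP 2.7.
2. Impute a missing start time as 00:00 and a missing end time as 23:59.
3. Do not substitute infusion start for untimed Day 1 adverse events. SAP 2.7 deliberately includes intra-surgery events before dosing and classes Day 1 by date. That substitution would mislabel them, and it would recreate a reversal whenever the recorded end precedes infusion.
4. Assign untimed Day 1 medications by recorded operative phase where it is collected; otherwise report them in a separate category for Day 1 with time unknown. The readable documents do not confirm a phase field for every drug, so the second route is needed.
5. Add a rule that no imputed start or end may make the end precede the start. This also covers EOS visits that fall after Day 90 within the window.

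The cost is SAP wording and derivation code. No new data are needed.
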